6.7 Early Termination Visit

All effort will be made to conduct an early termination visit for subjects who withdraw from the study. This visit will include all of the procedures performed at the normal end-of-study visit, with the exception of collection of plasma, urine, saliva, stool (optional), and vaginal secretion (optional) samples for PK analysis.

7 Study Procedures/Evaluations

7.1 Clinical Evaluations

At each study visit that requires a clinical assessment per protocol, the investigator will examine the patient and document the clinical signs and symptoms according to the scales described below.

Clinical Response Oropharyngeal/Esophageal Candidiasis:

The investigator will examine the oral cavity and question the subject to identify any signs/symptoms of infection and categorize clinical response to treatment.

The presence of plaques will graded according to the following scale, modified from an AIDS Clinical Trial Group (ACTG) Protocol:

- 0 None = Absent
- 1 Minimal = 1-5 discrete plaques and/or one confluent plaque ≤ 3 cm in longest length
- 2 Diffuse = Plaques that are more than minimal extent; or presence of ulcers
- 3 Worse = Plaques were clearly worse than on previous visit

The severity symptoms (dysphagia, odynophagia, retrosternal pain, oral pain, burning of mouth) will be graded according to the following scale:

- 0 None = Symptom was not present.
- 1 Mild = Symptom was present, but no or minimal interference was noted with eating.
- 2 Moderate = Symptom(s) present and led to interference with eating many foods.
- 3 Severe = Symptom(s) were very marked. The subject was unable to eat most foods.

The sum of the symptom scores will be used as the severity score.

Clinical Response Vulvovaginal Candidiasis:

The investigator will examine the patient and question the subject to identify any signs/symptoms of infection and categorize clinical response to treatment. The following signs and symptoms will be evaluated in each patient:

- Vaginal erythema
- Vulvovaginal pruritus
- Vaginal discharge

The severity of each symptom will be graded according to the following scale:

- 0 = Absent
- 1 = Mild
- 2 = Moderate
- 3 = Severe

The sum of the scores for all symptoms will be used as the severity score.

Clinical Response OMC:

The investigator will assess the signs and symptoms of OMC. For clinical response, the target thumbnail or great toenail will be assessed for the presence, absence, or improvement of OMC and subungual hyperkeratosis, and percentage of nail involvement will be estimated. Pictures will be taken every 2-weeks to document changes. The pictures will be taken by a medical photographer and will not contain identifiable information. Patients will sign the standard NIH photography consent form before pictures are taken, and may decline photography.

7.2 Endoscopic Evaluations

Patients with a diagnosis of EC will undergo a clinically indicated endoscopic evaluation under either conscious sedation or general anesthesia within 4 weeks before study drug initiation. These patients will also undergo a second endoscopy for research purposes only at end of treatment or within 4 weeks of clinical improvement, whichever occurs first. Each endoscopic evaluation will be graded according to the following scale:

• 0 None = Absent

- 1 Minimal = 1 to 5 discrete plaques and/or one confluent plaque ≤ 3 cm in longest length
- 2 Diffuse = Plaques that are more than minimal extent; or presence of ulcers
- 3 Worse = Plaques were clearly worse than on previous visit

7.3 Mycological Evaluations

All patients will undergo mycological evaluations at baseline and specified follow-up visits. Samples will be collected by swabbing the affected site. Portions of tissue leftover from clinically indicated biopsies may also be requested for mycological analysis. Results of mycological evaluations will be presented semi-quantitatively as:

- No growth
- One colony
- Scant
- Light
- Moderate
- Heavy
- Indeterminant: Extenuating circumstances preclude classification.

Measures of mycological response will include:

- Eradication: No growth.
- Partial response: Decrease in quantity of *Candida* from pre-treatment levels (eg, from heavy to scant).
- Persistence: No change or a worsening in Candida burden from pre-treatment levels.
- Relapse: A patient has achieved eradication or partial response initially, only to have the infection develop again after initial response or eradication.

7.4 Laboratory Evaluations

Stool, Saliva, and Vaginal Secretions

Stool, saliva, and vaginal secretions will be collected for PK analysis and may be used for other immunologic or microbiologic studies. Collection of stool and vaginal secretions is optional. Stool samples will be continuously collected (as available) for 24-hour PK analysis at the NIH Clinical Center on specified days. Saliva samples will be collected at pre-dose, 8 (± 3 hours) and 24 hours (± 1 hour) postdose for 24-hour PK analysis. Vaginal fluid will be collected by the

patient using the Instead™ Softcup (Evofem, Inc [San Diego, CA, USA]), a menstrual fluid collection device. The patient will insert the Softcup 24 hours postdose. After 2 hours, the patient will remove the cup and place it in a urine specimen container. There is a risk of dislodging an IUD with the Softcup; therefore, vaginal fluid collection will not be done in patients with IUDs. Vaginal fluid collection will be deferred during a patient's menstrual period and will not be done in patients who have had a hysterectomy with cervix removal.

In the study drug extension phase vaginal fluid will be collected by the subject using the Instead™ Softcup. The subject will insert the Softcup and remove it after 60 seconds and place it in a Falcon tube container. Vaginal collection is done unrelated to study drug administration time.

Urine

Urinalysis includes appearance, glucose, bilirubin, ketone, specific gravity, pH, protein, urobilinogen, nitrite, leukocyte esterase, white blood cell count, red blood cell count, hemoglobin.

Urine will also be continuously collected for 24-hour PK analysis on specified days.

Serum/Urine Pregnancy Test

A serum or urine pregnancy test will be given to women of childbearing potential as noted in the Study Schedule. Pregnancy prevention reminders and assessment of compliance will be done at each visit for subjects capable of becoming pregnant.

Blood Draws

Research evaluations on blood may include, but are not limited to, the following laboratory tests:

- PK
- Hematology: complete blood count with differential and platelet count
- Acute care panel, mineral panel, and hepatic panel

Plasma and PBMCs may be collected for storage. Plasma for 24-hour PK analysis (6 mL) will be collected in purple top K2-EDTA tubes at predose and 1 (± 5 minutes), 2 (± 5 minutes), 4 (± 15 minutes), 8 (± 15 minutes), Page 42 of 101

10 (± 15 minutes), 12 (± 15 minutes), and 24 hours (± 1 hour) postdose on specified days. Intravenous lines will be placed to facilitate multiple sample collections over 24 hours. Samples will be processed to measure plasma concentrations via a validated liquid chromatography with tandem mass spectrometry assay (LC-MS/MS).

8 Potential Risks and Benefits

8.1 Potential Risks

CAMB: There is limited experience in humans for the study drug. In the only clinical study on CAMB, side effects included nausea, abdominal pain, vomiting, and diarrhea. There was one instance of a moderate upper respiratory tract infection in a participant dosed with 800 mg of CAMB, but this was determined to not be related to CAMB. Risks associated with non-enchochleated formulations of AMB include nephrotoxicity, change in clotting factors, anemia, gastrointestinal intolerance, allergic reaction, or other unknown risks to this medication. These effects have not been observed in healthy humans dosed with CAMB. There is also the possibility that this treatment will have no effect on the fungal infection for which it is being used so the infection may worsen. It is possible that the Candida infecting or colonizing the study participant could become resistant to amphotericin due to the exposure to the study drug. This could limit treatment response to systemic intravenous amphotericin potentially in the future.

The effects of CAMB on the developing fetus are unknown. Therefore, patients must use appropriate and effective forms of contraception to avoid becoming pregnant or to avoid impregnating their partner.

Endoscopy and Biopsies: Diagnostic endoscopy when performed by a trained endoscopist is generally safe and well tolerated. Cardiopulmonary complications may account for over 50% of the reported complications, with the majority the result of aspiration, over-sedation, hypoventilation, vasovagal episodes, and airway obstruction. Significant complications can occur as a result of instrumentation, such as bleeding, perforation, and infection, with an overall frequency that approximates 0.1% for upper endoscopy. The risk of perforation and/or death is approximately 0.001%, but varies with the condition of the patient and performance of special procedures such as biopsy. These endoscopic complications were determined from elderly hospitalized patients, so the exact risk is unknown in the population for the current study.

NIH gastroenterologists have extensive experience with performing multiple endoscopic biopsies for research purposes and have found these well tolerated without appreciably increasing the risk of otherwise routine endoscopy. ¹³ In this work, they performed a retrospective review of 253 research endoscopies, for which an average of 38 biopsies was obtained per patient. No major complications were identified. Minor complications occurred and included self-limited bleeding and or pain in 5% of subjects. There was no statistically significant association between the number of biopsies, type of procedure, location of research biopsies and the risk of complications.

As a general practice, the risk of the procedure is minimized by monitoring pulse, blood pressure, and oxygen saturation throughout the procedure and by providing inpatient monitoring after the procedure.

In order to prevent complications and minimize their impact, we will avoid over-insufflation during biopsies, and provide post-procedure instructions for patients to recognize early warning signs of significant complications (eg, abdominal pain, fever, hematemesis, melena, chest pain and increased dysphagia) while providing mechanisms for early evaluation and treatment at the NIH CC (providing patient with contact information for on-call physician, study

team being available to address concerns, having emergency radiology, surgical consultation, and endoscopy available).

Conscious Sedation: Conscious sedation may be used in some patients undergoing endoscopy. Sedative drugs will be provided by CCMD and/or experienced anesthesiologists of the NIH CC. Side effects from sedative medications include cardiovascular and respiratory depression manifested by bradycardia, hypotension, respiratory acidosis, and apnea. Additional adverse reactions reported with these drugs are stinging or pain at the injection site, hiccoughs, nausea, vomiting, postoperative drowsiness and headache, and hypersensitivity reactions. Patients will be closely monitored and appropriate countermeasures will be taken as necessary.

General Anesthesia: General anesthesia may be used in some patients undergoing endoscopy and will be provided by CCMD and/or experienced anesthesiologists of the NIH CC. Common side effects include nausea, vomiting, mild allergic reactions, headache, and dizziness. Temporary confusion, lung infection, stroke, heart attack, or death are exceedingly rare side effects. Patients that undergo general anesthesia will be closely monitored during and after the procedure for adverse reactions.

Venous blood draw: Blood drawing may cause pain, bruising, lightheadedness, dizziness, possible fainting, local discomfort, bleeding, and, rarely, infection at the site where the needle is inserted. The amount of blood collected for research purposes under this protocol will not exceed the limits allowed for adult and pediatric research subjects by the NIH CC (http://cc-internal.cc.nih.gov/policies/PDF/M95-9.pdf). Additionally, at the time of enrollment, the study staff will ask each subject about their participation in other research studies to ensure the amount of blood drawn for research purposes does not exceed these guidelines.

Vaginal fluid collection using the Instead Softcup: Patient may experience pressure as the Instead Softcup is inserted into the vaginal cavity. The patient should not feel any discomfort during the secretion collection. The test is usually not painful. There is a risk of dislodging an IUD with the Instead Softcup, so vaginal fluid collection will NOT be done in patients with IUDs. There is also a risk of Toxic Shock Syndrome when the Instead Softcup is left in the vaginal

cavity for more than 12 hours. Patients will be instructed to remove the Instead Softcup after 1 to 2 hours.

Autoimmune Polyendocrinopathy-Candidiasis-Ectodermal Dystrophy

(APECED): APECED patients are hypoadrenal and therefore require stress-dose steroids for any procedure. The risks of inadequate steroid coverage are hypotension, circulatory collapse, and death. Patients will be closely monitored during steroid therapy, and any adverse reactions will be treated appropriately.

Photographs: Having pictures taken may be embarrassing to some people. These photographs may be published in medical journals, without identifying the participant. We will attempt to preserve the anonymity of the participant as much as possible, while providing the information needed to support the research being published. Participants may decline photographs or place any restrictions on their use. Participants will be given the opportunity to discuss this with the PI or AIs.

8.2 Potential Benefits

The individuals we will enroll on this study will be refractory or intolerant to standard non-intravenous treatment for mucocutaneous candidiasis infections. Patients may not directly benefit from participating in this study. However there is the potential benefit that access to this novel formulation of AMB may be effective treatment of the *Candida* infection and result in clinical improvement. The information obtained in this study may improve the investigators' understanding of the use of CAMB in treating people with refractory mucocutaneous candidiasis.

9 Research Use of Stored Human Samples, Specimens, or Data

Intended Use: Samples and data collected under this protocol may be used
to study drug levels in plasma, stool, urine, vaginal or salivary secretions to
understand the pharmacodynamics of the study drug. All of the patients will
be enrolled on other studies that allow for genetic studies, including whole
exome sequencing, so genetic studies will not be performed as part of this
study.

- located in a locked room with restricted access. Specifically, PK blood and data will be stored in the locked sample analysis/storage room (key required) of the Clinical Pharmacokinetics Research Laboratory inside of the Clinical Center Pharmacy Department, which is restricted by badge access to only pharmacy department employee. Stool, urine, vaginal and saliva samples will be stored in locked Freezer OP11 node 2 probe 88. Samples and data will be stored using codes assigned by the investigators. Data will be kept in password-protected computers. Only investigators will have access to the samples and data. Blood, stool, urine and saliva samples will be sent to Lambda Therapeutic Research, Inc. ([name]) for analysis. Vaginal samples will remain with the Fungal Pathogenesis Unit at NIH. PBMC specimen will be stored at the Neutrophil Monitoring Laboratory, Leidos Biomedical Research, Inc.
- Tracking: Samples will be tracked using a database located on a
 password-protected computer, which will be maintained by the investigators
 and their designees. Only investigators and their designees will have access
 to this database.

Disposition at the Completion of the Protocol:

In the future, other investigators (both at NIH and outside) may wish to use these samples and/or data for research purposes. If the planned research falls within the category of "human subjects research" on the part of the NIH researchers, NIH IRB review and approval will be obtained. This includes the NIH researchers sending out coded and linked samples or data and getting results that they can link back to their subjects. Any clinical information shared about the sample would similarly require before IRB approval.

Reporting the Loss or Destruction of Samples/Specimens/Data to the IRB:

Any loss or unanticipated destruction of samples (for example, due to freezer malfunction) or data (for example, misplacing a printout of data with identifiers) that meets the definition of a reportable event will be reported to the NIH IRB according to NIH Human Research Protection Program (HRPP) Policy 801.

Additionally, subjects may decide at any point not to have their samples stored. In this case, the principal investigator (PI) will destroy all known remaining samples and report what was done to both the subject and to the IRB. This decision will not affect the subject's participation in this protocol or any other protocols at NIH.

10 Remuneration Plan for Subjects

Subjects will be compensated for their time and inconvenience. Study subjects who complete all study procedures in a dosing cohort will receive \$520 plus \$200 for endoscopy (if indicated per protocol). Subjects who do not complete all study procedures will receive compensation based on the extent of their participation as follows: \$200 for the in-patient initial dosing study point and \$80 for the serial PK blood draw; \$40 for the 24 hour admission PK study point and \$80 for the serial PK blood draw; \$30 for each of 4 outpatient blood draws; \$200 for endoscopy, if indicated per protocol. There will be no compensation for the Extension phase of the study, although payment for travel-related expenses will be provided according to the NIAID Travel Policy. Payment will be issued following the end-of study visit. Volunteers who require additional dosing cohorts will receive compensation for the new cohort, as above.

11 Assessment of Safety

11.1 Toxicity Scale

We will utilize National Institute of Allergy and Infectious Diseases, Division of Microbiology and Infectious Diseases (DMID) Adult Toxicity Table (MODIFIED) (Appendix A).

11.2 Recording/Documentation

At each contact with the subject, information regarding AEs will be elicited by appropriate questioning and examinations. All events, both expected/unexpected and related/unrelated will be recorded on a source document. Source documents will include: progress notes, laboratory reports, consult notes, phone call

summaries, survey tools, and data collection tools. Source documents will be reviewed in a timely manner by the research team. All reportable AEs that are identified will be recorded in CRIMSON. The start date, the stop date, the severity of each reportable event, and the PI's judgment of the AE's relationship and expectedness to the study agent/intervention will also be recorded in CRIMSON.

11.3 Reporting Procedures

11.3.1 Reporting to the NIH IRB

Reportable events will be tracked and submitted to the NIH IRB as per Policy 801 (Appendix F) and Policy 802 (Appendix G).

11.3.2 Reporting to the NIAID Clinical Director

The PI will report unanticipated problems (UPs), major protocol deviations, and deaths to the NIAID clinical director according to institutional timelines.

11.3.3 Specific Adverse Event Reporting Requirements to the Sponsor

11.3.3.1 Serious Adverse Event Reporting

Any SAE that occurs after the consent is signed until 4 weeks after the last dose must be reported to Medpace Clinical Safety ("MedpaceSafety") whether or not it is judged related to the investigational product. All serious adverse events that the investigator considers related to study drug occurring 4 weeks after the last dose must be reported Medpace Safety.

Serious Adverse Event (SAE)

A Serious Adverse Event is an AE that results in one or more of the following outcomes:

- death.
- a life-threatening (i.e., an immediate threat to life) event
- an inpatient hospitalization or prolongation of an existing

hospitalization (see note below for exceptions)

- a persistent or significant incapacity or substantial disruption of the ability to conduct normal life functions
- a congenital anomaly/birth defect.

NOTE: The following hospitalizations are not considered SAEs in this clinical study:

- a visit to the emergency room or other hospital department lasting less than 24 hours that does not result in admission (unless considered an "important medical event" or a life-threatening event)
- elective surgery planned before signing consent
- admissions as per protocol for a planned medical/surgical procedure
- routine health assessment requiring admission for baseline/trending of health status (e.g., routine colonoscopy)
- medical/surgical admission for purpose other than remedying ill health state that was planned before study entry. Appropriate documentation is required in these cases.
- admission encountered for another life circumstance that carries no bearing on health status and requires no medical/surgical intervention (e.g., lack of housing, economic inadequacy, caregiver respite, family circumstances, administrative).

To report the SAE, fax or e-mail the completed SAE form to Medpace (fax number listed below) within 24 hours of awareness.

Medpace SAE reporting:

e-mail: [contact]

Medpace Clinical Safety, US

[contact], dial 3 or [contact], dial 3

[contact] **or** [contact]

The Investigator will provide, at a minimum, the protocol number, subject's initials, subject number, date of the SAE, SAE term, and relationship to

investigational product. Information identifying the subject must be obliterated before transmitting to Medpace Safety.

The PI will notify the IRB of the SAE according to its requirements. An initial report followed promptly by a complete report will be forwarded to the IRB, or in accordance with the IRB policy.

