11.7 Stopping Rules for an Individual Subject

A study subject will be discontinued from further study agent administration in the event of 1 or more of the following:

- Gastrointestinal toxicity (nausea/vomiting/diarrhea) that is interfering with the ability to perform regular every day activities.
- A subject experiences two Grade 3 events and/or one Grade 4 event that is possibly, probably, or definitely related to participation in the trial;
- SAE that is possibly, probably or definitely related to the study drug.
- Any laboratory abnormality, intercurrent illness, other medical condition or situation that occurs such that continued participation in the study would not be in the best interest of the subject.
- Any other events that the patient or investigators deems of clinical significance.

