 - 4.4.1. Major Deviations Deviations from the IRB approved protocol that have, or may have the potential to, negatively impact, the rights, welfare or safety of the subject, or to substantially negatively impact the scientific integrity or validity of the study.
 - 4.4.2. Minor Deviations Deviations that do not have the potential to negatively impact the rights, safety, or welfare of subjects or others, or the scientific integrity or validity of the study.
- 4.5. Reportable Event An event that occurs during the course of human subjects research that requires notification to the IRB. For the purposes of this policy, reportable events include non-compliance and unanticipated problems involving risks to subjects or others (also referred to as UPs), major deviations, deaths related or possibly related to research activities and new information that might affect the willingness of subjects to enroll or continue participation in the study.
- 4.6. Reviewing IRB The IRB responsible for reviewing human subjects research and determining that the research meets the required criteria for approval under the HHS regulatory requirements at 45 CFR 46 and, as applicable, the pertinent Subparts of 21 CFR.
- 4.7. Serious Adverse Event (SAE) -is any Adverse Event that:
 - Results in death:
 - Is life-threatening (places the subject at immediate risk of death from the event asit occurred);
 - Results in inpatient hospitalization or prolongation of existing hospitalization;
 - Results in a persistent or significant disability/incapacity;
 - Results in a congenital anomaly/birth defect; OR
 - Based upon appropriate medical judgment, may jeopardize the subject's health and may require medical or surgical intervention to prevent one of the other outcomes listed in this definition (examples of such events include allergic bronchospasm requiring intensive treatment in the emergency room or at home, blood dyscrasias or convulsions

NIH Intramural Research Program		
Office of Human Subjects Research Protections	Effective Date: 07/01/2019	
Reporting Research Events	Policy 801	Version: 1

that do not result in inpatient hospitalization, or the development of drug dependency or drug abuse).

In IND-regulated research, this term is used synonymously with serious

suspected adverse reaction. (See 21 CFR 312.32(a) for the FDA definition.)

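### The SAE list in section 11.3.3.1 omits the important-medical-event criterion that its own note and Appendix F use, so events serious only by medical judgment lose the 24-hour sponsor report and the SAE count

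*Combined protocol and SAP*

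**What the plan says.** Section 11.3.3.1 governs reporting to the sponsor's safety designee. It requires every SAE from consent until 4 weeks after the last dose to be reported, related or not, with the form sent within 24 hours of awareness. The definition begins "A Serious Adverse Event is an AE that results in one or more of the following outcomes". The outcomes are death, a life-threatening event, inpatient hospitalization or its prolongation, "a persistent or significant incapacity or substantial disruption of the ability to conduct normal life functions", and "a congenital anomaly/birth defect". The list ends there.

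A note then names hospital contacts that do not count as SAEs. One is an emergency-room or other hospital visit of under 24 hours without admission, but this exclusion is withdrawn if the event is life-threatening or is considered an "important medical event". Section 11 does not define that term.

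Policy 801 section 4.7, reproduced in Appendix F, gives a second SAE definition with the same five outcomes and a sixth: "Based upon appropriate medical judgment, may jeopardize the subject's health and may require medical or surgical intervention to prevent one of the other outcomes". Its examples are allergic bronchospasm treated intensively in the emergency room or at home, blood dyscrasias or convulsions without admission, and drug dependency or abuse.

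Several other rules use SAE status: follow-up reports within 24 hours of new information (11.3.3.2), the individual stopping rule (11.7, "SAE that is possibly, probably or definitely related to the study drug"), extension entry (6.6), notification to the safety monitoring committee (11.10.1) and the SAE count and percentage (13.3.2).

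**The concern.** The protocol holds two SAE definitions of different width, and a note that makes sense only under the wider one. The narrower one sits in the section that sets the sponsor's 24-hour clock, and it is the only definition in the protocol body. An investigator who follows it as written would not classify as an SAE an event that needed prompt intervention to avert a serious outcome but led to no admission.

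Timely safety reporting and a complete SAE summary are at stake. Section 8.1 says that human experience with the drug is limited, and it names allergic reaction and anemia among the risks of other amphotericin formulations. Under section 6.6 the extension can run to 60 months, with clinic visits spaced to every 12 weeks after the first month and laboratory work allowed locally. Treatment without admission is therefore plausible during that phase.

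**Working it through.** No sample size, power or rate enters this point, so the check compares the two texts and then traces each rule that uses SAE status.

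**Step 1. The two definitions side by side.**

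| Criterion | Section 11.3.3.1 | Policy 801, 4.7 |
|---|---|---|
| Death | yes | yes |
| Life-threatening | yes | yes |
| Inpatient hospitalization or prolongation | yes | yes |
| Persistent or significant incapacity | yes | yes |
| Congenital anomaly | yes | yes |
| Serious by medical judgment | **no** | yes |
| Total | 5 | 6 |

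The affected set is the difference between the columns: events that meet the sixth criterion and none of the other five.

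**Step 2. How the list and its note classify three kinds of event.**

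- *No admission, but life-threatening or incapacitating.* On the list and an SAE under both definitions. No gap.
- *Emergency visit under 24 hours, serious only by medical judgment.* The list does not include it. The note declines to exclude it. The two statements contradict each other, and the note leans towards inclusion.
- *Treated at home or in clinic, serious only by medical judgment.* The list does not include it, and the note, which concerns hospital contacts, does not reach it. Not an SAE under section 11.3.3.1; an SAE under Policy 801.

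**Step 3. Consequence for each rule in the third case.**

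| Rule | Result under the five-item list | Other route in the documents |
|---|---|---|
| Sponsor report, 24 hours (11.3.3.1) | not triggered | Policy 801, 5.1.3: no longer than 10 days |
| Committee notification as an SAE (11.10.1) | not triggered | only if also an unanticipated problem or IND safety report, or if a pausing, stopping or halting rule is met |
| SAE count and percentage (13.3.2) | not counted | appears under any AE and by System Organ Class |
| Stopping, SAE limb (11.7) | not met | Grade 4 limb; clinical-significance catch-all |
| Extension entry, SAE limb (6.6) | not met | Grade 4 limb |
| Halting (11.8) | unaffected | based on potassium and creatinine values |

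**Step 4. The reporting delay.** The clock moves from 24 hours (1 day) to at most 10 days, so the sponsor may learn of such an event up to 10 − 1 = 9 days later.

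**Step 5. The Grade 4 route.** Appendix A makes any clinical event that the clinician deems serious a Grade 4 event. One related Grade 4 event meets a stopping criterion in 11.7 and counts against extension entry in 6.6. Those two rules therefore largely reach the same result without the SAE limb. Grade 4 status does not, however, start the 24-hour sponsor clock or put the event in the SAE table. The Grade 4 limbs also require relatedness, whereas the sponsor report does not.

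**The case against.** The strongest reply is that the rest of the document already catches these events. Policy 801 section 5.1.3 obliges investigators in FDA-regulated studies to report SAEs to the sponsor, and that policy carries the six-item definition. Appendix A and the Grade 4 limbs protect the individual patient. The note shows that the authors meant to include important medical events. Accrual is closed, so few patients remain exposed.

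Much of this stands, and it rules out several stronger readings that a reader might infer:

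- *That such events never reach the sponsor.* Not supported, given the 10-day route. The 24-hour clock is what is lost. The same section of Policy 801 also tells investigators to report to the sponsor as the protocol describes, which leads back to the five-item list, so the policy does not restore the 24 hours.
- *That patients would go on being treated, or enter the extension, after such an event.* Largely not supported for related events, because of the Grade 4 limbs and the catch-all in 11.7.
- *That every example in Policy 801 section 4.7 is missed.* Not supported. Bronchospasm treated in the emergency room may fall under the note if the visit is under 24 hours, and some such events would be life-threatening or incapacitating and so already listed.
- *That the sponsor and the IRB would receive different expedited reports in general.* Too broad. Under Policy 801, SAEs that are not unanticipated problems go to the IRB only in summary at continuing review.
- *That the SAE percentage would shift by a known amount.* Not supported. No frequency is given, and the safety population is everyone dosed, which includes replaced patients and is not fixed at the planned 16 (the accrual ceiling is 20).

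Closed accrual limits the exposure but does not end it. Extension participants remain under SAE reporting until 4 weeks after the last dose, and the final SAE table is still affected.

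**Conclusion.** The point holds in a limited form. Section 11.3.3.1, its own note and Policy 801 section 4.7 disagree on what an SAE is. The stated rule in 11.3.3.1 misclassifies events that are serious only by medical judgment, mainly those treated outside an emergency visit; for emergency visits under 24 hours the text contradicts itself.

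In size, one of six criteria is missing. For the affected events the sponsor report may come up to 9 days later, they are not notified to the safety monitoring committee as SAEs, and they drop out of the SAE summary. The effect on individual stopping and extension entry is small, and the halting rule is untouched. How many patients this concerns cannot be derived from the documents.

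Two assumptions carry the conclusion: that the five-item list is complete as printed, of which there is no contrary sign, and that sections 11.10.1 and 13.3.2, which do not define the term, take their meaning of SAE from 11.3.3.1.

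**What to change.** Add the medical-judgment criterion of Policy 801 section 4.7 to the list in section 11.3.3.1, and state that this one definition applies to sponsor reporting, committee notification (11.10.1) and the SAE summary (13.3.2). The note then refers to a criterion that exists, and the protocol body agrees with Appendix F.

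Sections 6.6 and 11.7 use the same term, so their SAE wording must be reconciled with the amended definition. How those two clinical rules should treat such events is for the sponsor and the investigators to settle; this review does not propose an answer.

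The cost is one bullet in an amendment and possibly a few more expedited reports. AEs already recorded should be checked once against the added criterion before the SAE summary is produced.
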